11.4.4 Efficacy Evaluation

As indicated in Section 7, the first component of the co-primary endpoint is the percentage of subjects with sufficiently avid lesion(s) to be identified as a sstr2 positive lesion. This will be a simple percentage calculation (number of subjects in sstr2 positive population / number of subjects in ⁶⁸Ga-OPS202 screened population). The second component of the co-primary efficacy variable is the differences in the number of lesions detected by ⁶⁸Ga-OPS202 between the three PET acquisition timepoints (0.5, 1 and 2 hours) in the primary breast lesions. The second component of the co-primary efficacy variable will be summarised by each of the three PET acquisition timepoints (0.5, 1 and 2 hours). The results could identify that one, two or all three timepoints have equal validity for future studies in this population.

As indicated in Section 7, the secondary efficacy variables are the variables measured at Visit 2 after the i.v. administration of the IIP, listed below:

Key Secondary Endpoint:

- Differences in the number of lesions detected by ⁶⁸Ga-OPS202 between the three PET acquisition timepoints (0.5, 1 and 2 hours) and reader interpretation of optimal image(s) in nodular and metastatic lesions. Significant uptake of ⁶⁸Ga-OPS202 for the evaluation of a lesion is an avid lesion defined by the blinded readers at one of the acquisition timepoints as an easily identifiable lesion radiologically, where there has been clear focal uptake of ⁶⁸Ga-OPS202 and 1.5-fold or greater uptake than in the non-tumoural liver and lung parenchyma.
- The SUV_{mean} and SUV_{max} in the primary lesion between each of the three timepoints, measured in the most avid lesions (using the ⁶⁸Ga-OPS202 scans). This is assessed by

the tumour-to-background ratio in the primary tumour and each of the major anatomic sites (liver, lymph nodes, bone, lungs and brain); the background consists of non-tumoural liver parenchyma or aortic blood where sufficient liver is not available. Identification of lesions to be used will be made by one of the two primary readers.

Other Secondary Endpoints:

- Differences in relative lesion counts as a ratio of the number of lesions detected by ^{68}Ga -OPS202/ceCT at 0.5, 1 and 2 hours post dose respectively, compared to the number of lesions assessed by standard-of-truth (descriptive analyses). The standard-of-truth is the ^{18}F -FDG-PET/CT scan images acquired at any time during the study period (including the Screening period). This will be calculated by (number of lesions detected by ^{68}Ga -OPS202) / (number of lesions detected by ^{18}F -FDG-PET).
- Differences of absolute number of lesions between the three PET acquisition timepoints detected in each of the following anatomic sites:
 - Lymph nodes
 - Liver
 - Axial/appendicular skeleton
 - Lungs
 - Brain

The second component of the co-primary and appropriate secondary endpoints will also be evaluated on a radioactivity dose MBq/kg of body weight.

The secondary endpoints will be summarised by each of the three PET acquisition timepoints (0.5, 1 and 2 hours).

Exploratory Endpoints:

- Preliminary diagnostic sensitivity of ^{68}Ga -OPS202 imaging of breast cancer expressing sstr2 positive by both subject-based and lesion-based analysis compared to standard-of-truth
- SNR calculated from lesion-free volume of interest (VOI) in the liver: $\text{SUV}_{\text{mean}}/\text{SUV}_{\text{SD}}$ at the three PET acquisition timepoints
- Estimated correlation in terms of number of avid lesions between ^{68}Ga -OPS202 PET at the agreed “optimum timepoint” and ^{18}F -FDG-PET
- Estimated correlation between ^{68}Ga -OPS202 PET uptake and results of immunohistochemistry staining of sstr2 of the primary tumour.

For further details on efficacy endpoints, refer to Section 7 and the Imaging Review Charter (IRC).

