3.7 Stopping Rules and Discontinuation Criteria

During the conduct of the study, SAEs will be reviewed (see Section 8.1.3) as they are reported from the study centres to identify safety concerns. A specific site or a given cohort can be discontinued or the entire study may be terminated at any time if the sponsor judges it necessary for any reason. In that case, all scheduled procedures and assessments for subjects who are still in the study will be performed. Some possible reasons for the closure of a study site may include:

- failure of the Investigator staff to comply with the protocol or with the GCP guidelines
- safety concerns
- inadequate subject recruitment.

The study may be terminated by the sponsor at any time.

A subject may discontinue participation in the study at any time for any reason (e.g. withdrawal of consent, AE). The investigator and/or sponsor can withdraw a subject from the study at any time for any reason (e.g. protocol deviation as defined in Section 13.1.2, noncompliance with the protocol conditions or AE). All cases of discontinuation will be discussed between the investigator and the sponsor.

Futility Stopping Rule

If less than three sstr2 positive evaluable subject scans out of 30 consecutive subjects screened with ⁶⁸Ga-OPS202 PET/CT, or less than 8 out of 50, the study will be stopped.

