11.2 Sample Size Determination

It is anticipated that a total of approximately 54 subjects will be enrolled in the study for ⁶⁸Ga-OPS202 PET/CT imaging, to obtain around 16 sstr2 positive BC evaluable subjects. Considering the estimated prevalence of sstr2 overexpression in breast cancer, the overall number of subjects to be administered ⁶⁸Ga-OPS202 in the study will be over 50. However, when the ICL identifies 16 sstr2 positive evaluable subjects, with a minimum of two subjects with advanced disease, the study will be complete.

This estimation of 16 sstr2 positive BC evaluable subjects is considered appropriate for a descriptive analysis and it is not based on a formal statistical sample size calculation. In the event that a subject misses an imaging exam and/or measurement relevant to the primary and key secondary endpoints, an additional subject will be recruited as a replacement to ensure an adequate sample size in the sstr2 positive BC evaluable set.

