3.2.1.1 Primary efficacy analysis

First component of the co-primary endpoint

The first component of the co-primary endpoint is the percentage of subjects with sufficiently avid lesion(s) to be identified as a sstr2 positive lesion, i.e. the sstr2 positive prevalence in this study population. Avid is defined by the blinded readers at one of the timepoints as an easily identifiable lesion radiologically, where there has been clear focal uptake of ⁶⁸Ga-OPS202.

This will be a simple percentage calculation:

$$\begin{aligned} & \text{Percentage of subjects with avid lesion identified as sstr2 positive lesion} \\ &= \frac{\text{Number of subjects in sstr2 positive population}}{\text{Number of subjects in } ^{68}\text{Ga} - \text{OPS202 screened population}} \end{aligned}$$

A listing with the subjects in sstr2 positive population and the subjects in the ⁶⁸Ga-OPS202 screened population will be provided in order to allow computing this percentage.

Second component of the co-primary endpoint

The second component of the co-primary endpoint is based on both image quality and lesion count using the sstr2 positive evaluable population.

The selection of the optimal PET acquisition time will be done by choosing the timepoint with superior images based on overall image quality and observed higher number of lesions detected.

The number of lesions detected by ⁶⁸Ga-OPS202 in the primary breast lesions will be reported at each of the three PET acquisition timepoints (0.5, 1 and 2 hours).

Individual values of number of lesions detected by ⁶⁸Ga-OPS202 in the primary breast lesions (result from both readers as well as final result) will be listed by subject and by PET acquisition timepoint.

Image quality

After blinded reading, the readers will compare the three scans (the three acquisitions of ⁶⁸Ga-OPS202) contemporaneously for each subject and note which image(s), if any, provides superior images based on overall image quality and lesion count.

This qualitative assessment will be performed using a quality score.

For each PET/CT assessment, each independent blinded reader will perform a direct comparison of the three ⁶⁸Ga-OPS202 scans acquired at different times (0.5, 1 and 2 hours) in the primary breast lesions. The readers will be allowed to select whether one, two or all three acquisitions are optimal, attributing a score for each assessment. The readers will be blinded to timepoint sequence.

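### The first co-primary endpoint, sstr2 positive prevalence, is planned as a bare percentage with no interval; enrolment also stops on the outcome itself, which adds a small bias whose direction depends on the true prevalence

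*Protocol*

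**What the plan says.** Protocol section 2.2 lists the percentage of women with sstr2 positive lesions as the first co-primary objective. Section 11.4.4 gives its whole analysis: "This will be a simple percentage calculation", with the sstr2 positive population over the 68Ga-OPS202 screened population. Section 11.3 rules out formal tests and mentions no interval. The statistical part of the synopsis names mean, standard deviation, median and ranges only.

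SAP section 3.2.1.1 repeats the ratio and says that a listing of the two populations "will be provided in order to allow computing this percentage". SAP section 3.1.5, whose title includes estimation, names no interval either. The abbreviation CI is in the SAP's list of abbreviations but is not used in the visible analysis text. SAP section 3.2.4 does tabulate the number and percentage of subjects in each population.

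On size, Protocol section 11.2 says that "a total of approximately 54 subjects will be enrolled in the study", "to obtain around 16 sstr2 positive BC evaluable subjects", and that "it is not based on a formal statistical sample size calculation". On completion it says: "when the ICL identifies 16 sstr2 positive evaluable subjects, with a minimum of two subjects with advanced disease, the study will be complete". Section 3.7 adds a futility rule that starts "If less than three sstr2 positive evaluable subject scans out of 30 consecutive subjects screened with" 68Ga-OPS202, with a second limit of fewer than 8 out of 50. Neither document links these rules to how the percentage should be read.

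**The concern.** A proportion from about 54 subjects is imprecise, and this one answers a co-primary question. Given as a single figure, it can be carried into the planning of later studies as if it were well determined.

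Second, recruitment is not a fixed number of subjects. It ends when enough positives have been found, or when too few have. Under such rules positives divided by subjects imaged is generally not unbiased, so the size and direction of the bias need checking before anyone decides whether a different estimator is needed.

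**Working it through.** **Inputs.** From Protocol 11.2: about 54 subjects, 16 positives, at least two advanced. From Protocol 3.7: stop if fewer than 3 of 30 or fewer than 8 of 50. From Protocol 11.4.4: the estimator x/N. The prevalence behind the figure of 54 is mentioned ("Considering the estimated prevalence of sstr2 overexpression in breast cancer") but not given.

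**The planned size.** The expected number imaged to reach r positives at prevalence p is r/p. With an assumed p = 0.30, 16/0.30 = 53.3, which rounds up to 54. Read backwards, 16/54 = 29.6%. I use this as the implied prevalence.

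**Precision if 16 of 54 is observed.** The two-sided 95% Clopper-Pearson limits are beta quantiles:
- lower: 0.025 quantile of Beta(16, 39) = 18.0%
- upper: 0.975 quantile of Beta(17, 38) = 43.6%

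The width is 43.6 − 18.0 = 25.6 points and the half-width 12.8 points. The 95% level is my assumption, since the documents name none.

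**Bias from stopping.** I took E[x/N] as the sum of (x/n) × P(enrolment stops at x positives in n subjects), by exact recursion over all paths. With only the stop at 16, P(N = n) = C(n−1, 15) p^16 (1−p)^(n−16). The futility limits are applied at the 30th and 50th subject. This treats the positives in the numerator as the same subjects who trigger the stop, and leaves out the advanced-disease condition.

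| True prevalence | Stop at 16 only | All trials, with futility | Trials that reach 16, with futility |
|---|---|---|---|
| 10% | +0.6 | −1.3 | +3.8 |
| 16% | +0.9 | −1.0 | +2.9 |
| 20% | +1.0 | 0.0 | +2.2 |
| 25% | +1.2 | +0.9 | +1.6 |
| 29.6% | +1.3 | +1.25 | +1.4 |
| 40% | +1.5 | +1.5 | +1.5 |

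(Bias of x/N in percentage points.)

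At 29.6% with futility the root mean square error is about 7 points. The bias is therefore 1.25/7, about one fifth of the error, and 1.25/12.8, about one tenth of the half-width.

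**Advanced-disease condition.** By simulation without the futility rule, with an assumed advanced share of 5% to 30% and p from 20% to 40%, the bias is about +0.5 to +1.7 points. The picture does not change.

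**Does the ordinary interval still work?** With both futility limits, Clopper-Pearson coverage over all trials is 98.2% at a true 10%, 97.0% at 16%, 95.9% at 20%, 94.8% at 25% and 95.6% at 29.6%. Among only those trials that reach 16, coverage stays at about 95% or more from 15% upward. At 10% it drops to 85%, but only 12% of trials would get that far.

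**Would an inverse-sampling estimate do better?** If 16 of 54 is observed, (16−1)/(54−1) = 15/53 = 28.3%, with an exact inverse-sampling interval of 18.0% to 42.3%, close to the ordinary one. Without futility limits this estimate is unbiased. With them, using 15/(N−1) on reaching 16 and x/N otherwise moves the overall bias at 20% from 0.0 to −0.9 points, and at 16% from −1.0 to −1.5. Among trials that reach 16 it is still high, by 1.1 points at 20% and 1.9 at 16%.

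**The case against.** The strongest reply has four parts.

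- **The study is openly descriptive, with no tests and no formal sample size.** True, but an interval is estimation and not a test, so this does not excuse its absence. It does lower the stakes of a correction of about one point.
- **The counts will be available.** SAP 3.2.4 tabulates the two populations, so numerator and denominator are visible and a reader could derive an interval. That stands in part. The prevalence has no row of its own, and neither method nor confidence level is prespecified.
- **The SAP was cut down after premature termination with limited data (SAP section 5).** This explains the listing. It also means that the rule of 16 may not have ended enrolment, in which case the stopping bias worked out above may not apply. Fewer subjects make an interval more necessary: with assumed counts for illustration, 3/10 gives 6.7% to 65.2% and 6/20 gives 11.9% to 54.3%.
- **The bias is small and not always upward.** This stands in full.

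A reader might infer something stronger: that the percentage is systematically too high and should be replaced by (16−1)/(N−1) with a negative binomial interval. The documents do not support this. The futility stops retain low results and cancel or reverse the bias at about 20% and below. Nor is the numerator tied to 16: the trigger counts evaluable positives, who need at least two evaluable timepoints, and requires two advanced cases, while the numerator is the broader sstr2 positive population (Protocol 11.1, SAP 2.1.2 and 2.1.3). The numerator can exceed 16, and recruitment can run past the 16th positive.

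**Conclusion.** The point holds for the missing interval. A co-primary proportion is planned with no measure of uncertainty, although 16 of 54 would carry an exact 95% interval about 26 points wide.

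The stopping rules justify a caveat and no more: about +1.3 points at the implied prevalence of about 30%; about +2 to +3 points at a true 16% to 20% among trials that reach 16; about zero near 20% and slightly negative below it once futility stops are counted. The ordinary exact interval keeps about 95% coverage or more over all trials, so no special estimator is required.

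This rests on an implied prevalence that the documents do not state, on a 95% level, on futility looks at the 30th and 50th subject, and on treating trigger and numerator as the same subjects.

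**What to change.** In Protocol 11.4.4 and SAP 3.2.1.1:

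- Tabulate x, N and x/N for the sstr2 positive prevalence, with a two-sided exact (Clopper-Pearson) 95% interval, whatever ended enrolment.
- State beside it which rule or decision ended enrolment. If it was the rule of 16, note that the percentage tends to be slightly high. If it was futility, note that it tends to be low.
- Make any inverse-sampling estimate an optional sensitivity analysis at most. It should use the actual numerator and not a fixed 16.
- In Protocol 11.2, state the prevalence assumed behind the figure of 54.

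The cost is a few sentences and one table row, with no new data or subjects. The price in presentation is a visibly wide interval beside a co-primary result.

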11.4.5 Adjustment for Country/Centre Effect

Not applicable.

11.4.6 Safety Evaluation

All AEs will be coded according to the MedDRA version (latest version in use) and will be classified by MedDRA SOC and PT. AEs, SAEs, AEs leading to discontinuation of study treatment, and AEs leading to death will be summarised and listed by subject, SOC class and PT. Adverse events reported by investigators using the NCI-CTCAE classification (version 5.0) will be coded using MedDRA dictionary (latest available version).

Incidence of all reported AEs and SAEs will be tabulated. In addition, summary tables will be presented by maximum intensity, drug relationship and AEs associated with premature withdrawal of study medication.

Concomitant medication will be coded by using WHO Drug Dictionary (WHO-DD) (latest available version) and will be summarised.

Summary statistics (mean, median, SD and range as appropriate) will be presented for vital signs (including blood pressure and heart rate), ECG parameters, clinical laboratory tests etc. at each assessment with change from Baseline. For laboratory data, abnormal values will be flagged in the data listings and a list of clinically significant abnormal values will be presented. Clinically significant ECG findings will also be flagged. Shift tables will be presented of the number and percentage of subjects with low, normal or high values and normal or abnormal exams.

Summary incidence tables will be provided classified by SOC, PT, and associated NCI-CTCAE worst grade. In the event of multiple occurrences of the same AEs being reported by the same subject, the maximum intensity (Grade 5 > Grade 4 > Grade 3 > Grade 2 > Grade 1 > missing > not applicable) will be chosen.

Haematological and biochemistry toxicities will be recorded and graded according to the NCI-CTCAE criteria. The NCI-CTCAE grade 3 and 4 haematology and biochemistry parameters by subject and by cycle will be listed. For WBC, neutrophils, platelets and haemoglobin, with associated grade 3 or 4 toxicities, nadir and day to nadir will be calculated.

11.5 Subgroup Analyses

Not applicable.

11.6 Interim Analyses

No interim analysis will be performed.

12 DIRECT ACCESS TO SOURCE DATA AND DOCUMENTS

Authorised personnel from external CAs and sponsor-authorised Quality Assurance personnel may carry out inspections and audits. The purpose of an audit is to ensure that ethical, regulatory and quality requirements are fulfilled in all studies performed by the sponsor.

Sponsor-delegated Clinical Research Associates will have access to source data and documents for source data verification purposes during monitoring visits.

Auditors and inspectors must have direct access to study documents and site facilities as specified in Section 13.4, and to any other locations used for the purpose of the study in question (e.g. laboratories).

In the event of the site being notified directly of a regulatory inspection, the investigator must notify the sponsor's representative as soon as possible, to assist with preparations for the inspection.

13 QUALITY CONTROL AND QUALITY ASSURANCE

13.1 Protocol Amendments and Protocol Deviations and Violations

13.1.1 Protocol Amendments

No changes from the final approved (signed) protocol will be initiated without the prior written approval or favourable opinion of a written amendment by the IEC, except when necessary to eliminate immediate safety concerns to the subjects or when the change involves only logistics or administration. In the event that an amendment to this protocol is required, it will be classified into one of the following three categories:

- **Non-substantial amendments** are those that are not considered ‘substantial’ (e.g. administrative changes) and as such only need to be notified to the IECs or regulatory authorities for information purposes.
- **Substantial amendments** are those considered ‘substantial’ to the conduct of the clinical study where they are likely to have a significant impact on:
 - the safety or physical or mental integrity of the subjects;
 - the scientific value of the study;
 - the conduct or management of the study; or
 - the quality or safety of the study drug used in the study.

Substantial amendments must be submitted to and approved by the IECs and relevant regulatory authorities, according to local regulations, prior to implementing changes.

Urgent amendments are those that require urgent safety measures to protect the study subjects from immediate hazard and as such may be implemented immediately by the sponsor with subsequent IECs and regulatory authority notification, forthwith.

The principal investigator and the sponsor will sign the protocol amendment.

13.1.2 Protocol Deviations

All protocol deviations will be identified and recorded by the sponsor or sponsor’s representative.

A major protocol deviation is any significant divergence from the protocol, i.e. nonadherence on the part of the subject, the investigator, or the sponsor to protocol-specific inclusion/exclusion criteria, primary objective evaluation criteria, and/or GCP guidelines.

Generally, a protocol deviation qualifies as major if:

- The deviation has harmed or posed a significant or substantive risk of harm to the research subject
- The deviation compromises the scientific integrity of the data collected for the study
- The deviation is a willful or knowing breach of human subject protection regulations, policies, or procedures on the part of the investigator(s)
- The deviation involves a serious or continuing noncompliance with any applicable human subject protection regulations, policies, or procedures
- The deviation is inconsistent with Ipsen’s research, medical and ethical principles.

See Section 11.1.2 for details on the impact of major protocol deviations on the inclusion of subjects in each analysis population.

A minor protocol deviation is any significant divergence from the protocol that does not impact the study results.

As a matter of policy, the sponsor will not grant exceptions to protocol specific entry criteria to allow subjects to enter a study. If under extraordinary circumstances such action is considered ethically, medically, and scientifically justified for a particular subject, prior approval from the sponsor and the responsible IRB/IEC, in accordance with the Standard Operating Procedure (SOP), is required before the subject will be allowed to enter the study. If investigative centre personnel learn that a subject who did not meet protocol eligibility criteria was entered in a study (a protocol violation), they must immediately inform the sponsor. Such subjects will be discontinued from the study, except in an exceptional instance following review and written approval by the sponsor and the responsible IRB/IEC, according to the applicable SOP.

